NCT number: NCT05366842

Study title: Assessment of clinical outcomes post application of StravixPL for robotic prostatectomy

Date of the study protocol: 7/03/2023

Johns Hopkins Medicine - eIRB Protocol (eForm A)

- Assessment of clinical outcomes post application of StravixPL for robotic prostatectomy

7/03/2023

1. Abstract

Erectile dysfunction is common in patients undergoing radical prostatectomy for prostate cancer and is thought to result from disruption of normal blood and nerve supply to the penis. There have been significant advances in surgical technique, including nerve sparing prostatectomy, as well as post prostatectomy penile rehabilitation, which have improved erectile recovery after surgery. Clinical use of growth factors and anti-inflammatory substances for prostate neurovascular bundle regrowth have emerged as a new technique to further enhance recovery of potency and potentially continence after prostate surgery. Patel et al. studied outcomes after placement of a dehydrated chorionic allograft membrane on neurovascular bundles during prostatectomy and reported that 65.5% of patients with moderate to high preoperative sexual function had return to potency at 8 weeks vs. 51.7% of patients with standard care¹. The mean time to recovery was 1.34 months¹. Johnson et al. compared viable to nonviable dehydrated placenta for chronic wounds and showed superior outcomes with viable tissue².

Surgical implantation of Stravix (Smith and Nephew. Columbia, MD), a lyopreserved placental tissue (LPT) is now FDA approved and has been used extensively in wound care. The use is expanding and more recently, LPT has been used in the management of diabetic foot ulcers, acute and chronic surgical wounds, various fistulas and even as a nerve wrap on the common peroneal nerve (Rodriguez, Foot and Ankle, 2017)³.

We intend to study whether placement of LPT over the spared neurovascular bundles during nerve-sparing prostatectomy will improve return to potency and/or continence after radical prostatectomy for prostate cancer. This research could provide a potentially meaningful advancement in quality of life outcomes for patients undergoing radical prostatectomy for prostate cancer.

2. Study Procedures

This is a single center, randomized; singe blinded, two-arm trial comparing the effects of direct placement of LPT over the spared neurovascular bundles vs. standard care (no placement of tissue) on erectile recovery and quality of life in patients undergoing bilateral nerve sparing radical prostatectomy for prostate cancer.

VCUT for Erectile Recovery During Bilateral Nerve Sparing RRP Protocol												
	Consult	Baseline Eval	Surgical Day	Post Op Day 1	2 weeks Post Op	1 Month Post Op	3 months Post Op	6 months Post Op	9 months Po	12 months Post Op	18 Months Post Op	
Informed Consent	x											
Medical Clearance		x										
IIEF	x				x	x	x	x	x	x	x	
SEQ	x				x	x	x	x	x	x	x	
EPIC, SF12, AUA SI	x				x	x	x	x	x	x	x	
Randomization	x											
Rx (PDE5i)					x							
AE Monitoring		x	x	x	x	x	x	x	x	x	x	
PSA Monitoring						x						

The sample size will be 10 patients randomized to each study arm (20 patients total). Study procedures will involve screening and informed consent after initial consultation, baseline evaluation including medical clearance and completion of validated questionnaires, and randomization.

In order to minimize the need for research-only in-person visits, telemedicine visits may be substituted for in person clinical trial visits or portions of clinical trial visits where determined to be appropriate and where determined by the investigator not to increase the participant's risks. Prior to initiating telemedicine for study visits the study team will explain to the participant, what a telemedicine visit entails and confirm that the study participant is in agreement and able to proceed with this method. Telemedicine acknowledgement will be obtained in accordance with the Guidance for Use of Telemedicine in Research. In the event telemedicine is not deemed feasible, the study visit will proceed as an in-person visit. Telemedicine visits will be conducted using HIPAA compliant method approved by the Health System and within licensing restrictions

Assessment tools will consist of the following questionnaires, *which will be administered online using a REDCap site hosted by the Data Informatics Services Core within the Johns Hopkins Biostatistics Center or via mail per patient preference*: IIEF questionnaire, the Quality of Erection Questionnaire (SEQ), and the version of the Expanded Prostate Cancer Index Composite (EPIC) that combines the Short Form Health Survey (SF-12) and AUA Symptom Index (AUA-SI). Standard practice associated with surgery, blood transfusion and postoperative laboratory testing will be performed. Operating room time, estimated blood loss, surgical margin status and length of hospital stay will be recorded. Patients will be prescribed a phosphodiesterase type 5 inhibitor (sildenafil, tadalafil or vardenafil) at 1 month following surgery to be used as conventional "on-demand" therapy. Adverse event monitoring will be performed. PSA monitoring is recommended at 3 and 12 months with the definition for biochemical recurrence set as a PSA of 0.2ng/mL (rising from an undetectable level after surgery).

3. Inclusion/Exclusion Criteria

Inclusion Criteria:

1. Male sex 40 to 70 years of age with localized prostate cancer (clinical stage less than or equal to T2a, Gleason grade less than or equal to 3+4=7, including 4+3=7 (Gleason 8 will be excluded), PSA less than or equal to 20 ng/mL)
2. Scheduled to undergo curative radical prostatectomy applying bilateral nerve-sparing procedure
3. Intact pre-surgical erectile function (International Index of Erectile Function [IIEF]-5 / Sexual Health Inventory for Men (SHIM) score greater than or equal to 18)
4. Willingness to attempt intercourse at least 5 times per month following surgery.
5. Has a sexual partner of at least 6 months with current sexual activity (within the past 4 weeks)

Exclusion criteria:

1. Known penile deformity or a history of Peyronie's disease
2. Pre or postoperative androgen therapy
3. Pre or postoperative radiation therapy
4. History of high or low blood pressure that is not controlled
5. Taking nitrates medications
6. History of heart problems such as angina, heart failure, irregular heartbeats, or myocardial infarction
7. History of drug or alcohol abuse
8. Current smoker has a 20 pack/year history of cigarette smoking
9. History of acute or chronic depression
10. History of liver problems or kidney problems
11. History of retinitis pigmentosa or severe vision loss, including a condition called NAION
12. History of spinal trauma or surgery to the brain or spinal cord
13. Other contraindications to the use of PDE 5 inhibitors
14. History of known sensitivities to any of the following reagents used for processing, disinfection, and storage, which may remain on the product:

- **Lyopreservation Solution:** 18.9% w/v Trehalose in Dulbecco's Phosphate Buffered Saline
- **Disinfection Solution:** 0.5% v/v Gentamicin Sulfate, 0.1% v/v Vancomycin reconstituted in Water for Injection (WFI), 1% v/v Amphotericin B, 98.4% Dulbecco's Modified Eagle's Medium (DMEM)
- **Processing Solution:** DMEM, Dulbecco's Phosphate Buffered Saline (dPBS), 11% Anticoagulant Citrate Dextrose Solution in Saline, Formula A (ACD-A), 1.7% w/v Trehalose in Dulbecco's Phosphate Buffered Saline

4. Drugs/Substances/Devices

a. The rationale for choosing the drug or substance dose or for choosing the device to be used.

Stravix (Smith and Nephew. Columbia, MD) is a Lyopreservation placental tissue that is FDA approved for homologous use as a wound cover or surgical wrap. There are no known contraindications to the use of Stravix. The product is available for use at Johns Hopkins and has been used by the pediatric urology department in the management of rectovaginal fistula⁴ it has also been used by the colorectal surgery department. Novel clinical use of growth factors and anti-inflammatory substances for prostatic neurovascular bundle regeneration has been shown with the use of a dehydrated human chorion membrane¹. Chronic wound studies have shown viable chorionic tissue, such as Stravix, to be superior to non-viable dehydrated chorionic tissue². We plan to prospectively study surgical placement of Stravix directly to neurovascular bundles and assess for improvement in erectile recovery as well as quality of life after radical prostatectomy for prostate cancer.

5. Study Statistics

The primary outcome variable is the patient's score on the IIEF questionnaire (erectile function domain) at 1,3, 6, 9, 12 and 18 months post-surgery. Comparison of changes in initial IIEF score will be evaluated to determine treatment efficacy. We anticipate a gradual increase in baseline IIEF score over the course of the study. The secondary outcome variables will be the patient's scores on the QEQ, combined EPIC/SF-12/AUASI questionnaires, other domains of the IIEF questionnaire. For statistical analysis based on ANOVA, the sample size is powered for a power of 80% with one-sided alpha of 0.05 showing a sample size of 23 patients in each arm is necessary to detect an expected difference of 5 points in IIEF scores (i.e. 20 vs. 15) at 6 months post-surgery. Therefore, the study is planned to enroll 30 patients in each arm. This sample size will accommodate dropout rate during follow-up.

6. Risks

Completion of the questionnaires and administration of Stravix are the only 2 procedures from this protocol that are outside of the realm of standard of care for the radical prostatectomy patient. All of the participants will be exposed to the questionnaires pre operatively and can assess whether they are willing to complete the trial, which will include 6 additional administrations of the questionnaires. If the questionnaires cause any type of discomfort or uneasiness at that time or any time during the study, the participant can decide to end their involvement with the protocol.

There are no contraindications to the use of Stravix. Smith and Nephew (Columbia, MD) reports that the product has been directly applied to spared neurovascular bundles in approximately 250 radical prostatectomies. Tissue donor screening methods are limited; therefore, certain diseases may not be detected.

The following complications of tissue transplantation may occur:⁵

- Transmission of diseases of unknown etiology;
- Transmission of known infectious agents including, but not limited to, viruses, bacteria, and fungi;
- Immune rejection of implanted Stravix®; or
- Loss of function and/or integrity of Stravix® due to resorption, fragmentation, and/or disintegration.

The occurrence of any serious adverse effects will end the patient's participation in the study and halt enrollment in the study to determine the safety of continuing the study. Each and every possible adverse effect of LPT will be investigated and treated individually to minimize the participant's discomfort. The safety of having the individual complete the study will also be assessed on an individual basis. At any time the participant can decide to terminate his participation in the study and no penalty or loss of benefits to which they are entitled.

The risks of radical prostatectomy will apply to both groups. These include but are not limited to bleeding, infection, and injury to surrounding structures. Rare complications include rectal injury requiring fecal diversion and acute blood loss anemia requiring transfusion. An ejaculation is expected. Late complications include urinary incontinence, erectile dysfunction, urethral stricture disease, and bladder neck contracture.

7. Confidentiality

Paper consent forms, enrollment check sheets, and other source or study documentation will be kept in a study binder. This binder will be stored in a locked office available only to the study team. Electronic data will be housed in a secure password protected REDCap database maintained by the Data Informatics Services Core within the Johns Hopkins Biostatistics Center. Only the study team will have access to this secure database. Of note, to maintain the protected health information of patients enrolled in this study, only the study Principal Investigator and primary coordinators will have the ability to export data containing identifying information from this master database. For the purposes of analysis, only de-identified data will be exported.

8. Benefits

The patient's conditions may improve as a result of participation in this study, specifically as related to erectile function and quality of life. However, there is no guarantee of this. The information from this research study may lead to a better treatment in the future for people with prostate cancer. The patients may not benefit from participation in this study. Their conditions may not get better or may become worse while they are in this study.

9. Payment and Remuneration

There will be no payment or remuneration for the participants in this study.

10. Costs

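### Section 2 randomises 10 patients per arm, but Section 5 requires 23 and plans 30; at the Section 2 size, power for the 5-point difference is about 48%, not 80%

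*Combined protocol and SAP*

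**What the plan says.** Two sections of the combined protocol and SAP set the size of the trial.

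- **Section 2, Study Procedures:** "The sample size will be 10 patients randomized to each study arm (20 patients total").
- **Section 5, Study Statistics:** for 80% power at a one-sided 0.05 level, the requirement is given in these words: "showing a sample size of 23 patients in each arm is necessary to detect an expected difference of 5 points in IIEF scores". The expected means are 20 and 15 at 6 months after surgery. The section concludes: "Therefore, the study is planned to enroll 30 patients in each arm". It adds that this number allows for dropout.

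Section 5 names ANOVA as the basis of the calculation. It gives no SD for the IIEF score and no dropout rate. No section describes a pilot phase, an interim stage or a reduction in enrolment that would explain how 10 and 30 per arm can both be the plan.

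**The concern.** Both numbers are written as the current plan, and they differ threefold: 2 × 10 = 20 patients against 2 × 30 = 60. Ten per arm is also less than half of the 23 per arm that Section 5 calls necessary, before anyone is lost to follow-up.

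The enrolment number decides when recruitment stops, how many men receive the tissue and what the result can show. If the team follows Section 2, the trial closes at 20 patients under a protocol that still contains an 80% power statement. A non-significant result could then be taken as evidence against a 5-point benefit when the chance of detecting that benefit was close to even. If the team follows Section 5, it enrols three times the number given in the procedures section. The document does not show which number governs.

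**Working it through.** **Inputs**

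| Quantity | Value | Source |
|---|---|---|
| Patients per arm | 10 | Section 2 |
| Patients per arm needed | 23 | Section 5 |
| Patients per arm to be enrolled | 30 | Section 5 |
| Power, alpha | 80%, one-sided 0.05 | Section 5 |
| Difference | 20 − 15 = 5 points at 6 months | Section 5 |
| Test | ANOVA; with two arms, equivalent to the two-sample t-test | Section 5 |
| SD | not stated | back-solved below |
| Dropout rate | not stated | 1 − 23/30 = 23.3%, implied by Section 5 |

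**Step 1: the plan's own figure.** Without an SD, 23 per arm cannot be reproduced independently. It can be inverted. Power is the probability that a noncentral t variable with 2n − 2 degrees of freedom and noncentrality d × √(n/2) exceeds the one-sided 5% critical value, where d = 5/SD. Setting power to 0.80 at n = 23 (44 df) gives SD = 6.71, so d = 5/6.71 = 0.745.

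The normal approximation, SD = 5 / [(1.645 + 0.842) × √(2/23)], gives 6.82. Because 23 is a rounded-up integer, the SDs for which it is the smallest sufficient number run from 6.56 to 6.71 (t) or from 6.67 to 6.82 (normal).

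**Step 2: power at other sizes, with d = 0.745 (t-test, one-sided 0.05).** At n = 10 the noncentrality is 0.745 × √5 = 1.67 on 18 df.

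| Evaluable per arm | Power |
|---|---|
| 7 | 37.1% |
| 8 | 41.0% |
| 10 | 48.3% |
| 23 | 80.0% |
| 30 | 88.6% |

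At the low end of the compatible SDs, power at 10 per arm is 49.8% (t, SD 6.56). The normal approximation gives 49.8% (SD 6.82) to 51.3% (SD 6.67). The rows for 7 and 8 apply the implied dropout to Section 2: 10 × 23/30 = 7.7.

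**Step 3: what 10 per arm can detect, at SD 6.71.**

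- Difference detectable with 80% power: 7.8 points.
- Smallest observed difference reaching one-sided p < 0.05: 1.734 × 6.71 × √(2/10) = 5.2 points. At the lowest compatible SD it is 1.734 × 6.56 × √(2/10) = 5.09. An observed difference equal to the expected 5 points would therefore not be significant.

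**Step 4: SD as a free assumption.** If Section 5's 23 per arm is set aside, one-sided t-test power at 10 per arm is:

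| Assumed SD | Power at 10 per arm |
|---|---|
| 5 | 69.4% |
| 6 | 55.9% |
| 7 | 45.7% |
| 8 | 38.2% |
| 10 | 28.5% |

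None of these reaches 80%.

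**The case against.** The strongest reply is that Section 5 attaches 80% power to 23 evaluable patients per arm, and no sentence claims 80% for 10. On that reading the power calculation is not wrong; the document carries two irreconcilable sample sizes, and if Section 5 is the operative text there is no shortfall. This stands as a description of the defect. It does not remove it, because the only power statement in the protocol is not met at the size Section 2 sets.

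A second reply is that the SD is back-solved, so 48% depends on a calculation that cannot be verified. That is correct, and the figure should be read as implied by the plan's own 23 per arm. It needs no outside SD, however: sample size, power and alpha together fix the standardised difference, and that fixes the power at 10 per arm.

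Third, the threshold for significance is not above 5 points under every assumption. With SD 6 it is 1.734 × 6 × √0.2 = 4.65, and with a normal cutoff at SD 6.67 it is 1.645 × 6.67 × √0.2 = 4.91. But SD 6 would give a requirement of 18 per arm by the normal formula, not 23, and ANOVA with 10 per arm uses the t cutoff on 18 df. At every SD compatible with 23 per arm, the t-based threshold stays above 5.

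Two smaller points are fair. The 23.3% dropout is an inference and may partly reflect rounding up to 30, so the 37% to 41% figures are illustrative. Nothing in the document calls the trial a pilot, so that label is optional.

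**Conclusion.** The concern holds. The protocol gives 20 patients in one section and 60 in another, and its 80% power claim is not met at the Section 2 size. Taking Section 5's own figures as correct, power at 10 per arm is about 48% (up to 49.8% by the t-test if 23 was rounded up, and up to about 51% by the normal approximation). The detectable difference is 7.8 points instead of 5. These figures assume a one-sided two-sample t-test, equal arms and no dropout; any loss lowers the power. They apply only if Section 2 governs. The contradiction itself rests on no assumption and must be fixed.

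**What to change.** Put one enrolment number in Sections 2 and 5. In either case, state the SD used, its source and the dropout rate assumed.

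- **If 20 is the target:** remove the text on 80% power, 23 per arm and 30 per arm. State instead the power for 5 points and the detectable difference at 10 per arm, recomputed with the sponsor's own SD (about 48% and 7.8 points at the implied SD of 6.7). Say that the result will be reported as an estimate with a confidence interval. Calling the trial a pilot would be consistent with this but is not required.
- **If 60 is the target:** correct the Section 2 figure to 30 per arm.

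The cost is protocol wording. With 20, the stated power becomes less favourable; with 60, Section 2 rises to a number that Section 5 already plans. Neither choice adds patients beyond those already written into the protocol.

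### Randomisation is scheduled at Consult, and nothing requires the arm to be withheld from the operator until the bundles are dissected; open the allocation only after each side's sparing is recorded

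*Combined protocol and SAP*

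**What the plan says.** All references are to the combined protocol and SAP.

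- **Timing.** In the section 2 schedule table, the row "Randomization x" has its only mark in the first visit column, Consult. Surgical Day is the third column and has none. The paragraph below the table gives the sequence as "screening and informed consent after initial consultation, baseline evaluation including medical clearance and completion of validated questionnaires, and randomization". It does not mention surgery, but it groups randomisation with the work-up.
- **Masking and comparison.** Section 2 calls the study a "single center, randomized; singe blinded, two-arm trial" and does not name who is blinded. The comparison is "direct placement of LPT over the spared neurovascular bundles vs. standard care (no placement of tissue"), so there is no sham.
- **Population.** Section 2 describes the effect of interest "in patients undergoing bilateral nerve sparing radical prostatectomy for prostate cancer". Inclusion criterion 2 in section 3 asks only that the man be "Scheduled to undergo curative radical prostatectomy applying bilateral nerve-sparing procedure".
- **Operative data.** Section 2 states: "Operating room time, estimated blood loss, surgical margin status and length of hospital stay will be recorded". Whether each bundle was spared is not on that list.

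The document does not say who holds the allocation, when the operator learns it, or what happens to a randomised man whose bundles are not both spared.

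**The concern.** The abstract attributes erectile dysfunction after prostatectomy to damage to the blood and nerve supply, and credits nerve-sparing technique with better recovery. The operator therefore controls a step that affects the primary outcome, the erectile function domain of the IIEF. An operator who knows the arm during dissection may handle the bundles differently by arm, even without meaning to. Blinding the patient does not prevent this. Analysing men as randomised does not remove it either, because the difference would be part of what each arm received.

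There is a second consequence. LPT presupposes a spared bundle, yet men enter the randomised set on the strength of planned sparing. Without a rule, the team must decide case by case whether to place tissue and whether to analyse a man in whom sparing failed. Excluding him after randomisation risks selection, particularly if knowledge of the arm influenced the sparing. Keeping him is valid, but it dilutes the effect and answers a question about planned rather than achieved sparing.

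**Working it through.** **1. The text.** The table puts randomisation at Consult. The paragraph puts it after clearance and questionnaires. They differ on order, and nothing here depends on that difference, because both read naturally as preoperative. With no sham, the operator must know the arm by the moment of placement. The open question is how much sooner, and no section answers it.

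**2. The plan's own figure.** Section 5 states that a "sample size of 23 patients in each arm is necessary to detect an expected difference of 5 points in IIEF scores" (20 versus 15 at 6 months), with 80% power and one-sided alpha 0.05. It gives no SD, so 23 cannot be reproduced directly. I solved for the SD using the two-sample noncentral t:

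power = P(T > t[0.95, 2n−2]), where T has 2n−2 degrees of freedom and noncentrality λ = δ / (SD × √(2/n)).

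Setting n = 23, δ = 5 and power = 0.80 gives SD = 6.71. Check: 6.71 × √(2/23) = 1.98; λ = 5/1.98 = 2.53; power = 80%. Any SD from 6.56 to 6.71 makes 23 the smallest adequate n.

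**3. Illustration of handling bias.** Assume no true effect and a shift of b points towards LPT caused by handling, and put δ = b in the formula. The shifts are assumptions. One-sided false-positive rate (nominal 5%):

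| Per arm | b = 0.5 | b = 1 | b = 2 |
|---|---|---|---|
| 10 | 6.9% | 9.3% | 15.8% |
| 23 | 8.1% | 12.6% | 25.8% |
| 30 | 8.7% | 14.1% | 30.7% |
| 30, SD 8 | 8.0% | 12.2% | 24.6% |
| 30, SD 10 | 7.3% | 10.3% | 19.0% |

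The direction is assumed too. If the operator took more care with controls and the true effect were 5 points, a 1-point shift the other way would leave an apparent difference of 5 − 1 = 4. Power would then be 73.8% at 30 per arm, against 88.6% without the shift.

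**4. Illustration of incomplete sparing.** Let a fraction q lack bilateral sparing; 5, 10 and 20% are assumed, because the document gives no rate. SD is 6.71 and follow-up dropout is ignored.

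- Kept, no effect in them: δ = 5(1 − q) = 4.75, 4.5, 4.0.
- Kept, half the effect in them: δ = 5(1 − 0.5q) = 4.875, 4.75, 4.5.
- Excluded: n(1 − q) per arm, δ = 5 (power loss only; selection is not quantified).

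| Per arm | q = 0 | Kept, no effect (5/10/20%) | Kept, half effect (5/10/20%) | Excluded (5/10/20%) |
|---|---|---|---|---|
| 10 | 48.3% | 45.1/42.0/35.8% | 46.7/45.1/42.0% | 46.5/44.7/41.0% |
| 23 | 80.0% | 76.3/72.3/63.5% | 78.2/76.3/72.3% | 78.1/76.1/71.6% |
| 30 | 88.6% | 85.6/82.1/73.8% | 87.2/85.6/82.1% | 87.1/85.4/81.5% |

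Three sizes are shown because section 2 gives 10 per arm, while section 5 gives 23 as the number needed and 30 as planned enrolment. That conflict is a separate matter, and it accounts for the low power in the first row.

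**The case against.** The strongest reply is that silence is not disclosure. A list can be generated early and opened late, and a Consult mark is compatible with that. This stands: a reader might infer that the operator will know the arm before dissection, and the document does not say so. What remains is a missing safeguard in a trial whose operator cannot be masked at placement.

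Next, the bias is assumed. Nothing shows that dissection would depend on the arm, and these are cancer operations with margin status recorded, which limits the freedom to vary technique. This also stands as regards size and direction. It does not remove the opportunity.

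A reader might also infer from the tables that handling bias matters more than dilution, because at 30 per arm power stays above 80% in all but one scenario. That does not follow. Section 5 adds the patients above 23 to cover dropout, and at 23 every incomplete-sparing scenario falls below 80%. Power loss and false-positive rate are also not on one scale.

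Incomplete sparing may be uncommon in men limited to T2a or lower, with Gleason 8 excluded, PSA of 20 or less and bilateral sparing already scheduled. Planned sparing is a legitimate target population, so restricting to achieved sparing is partly a choice of estimand. Finally, routine surgical notes may hold sparing status even though the list of study items does not. These points lower the weight of the second consequence. They do not supply a rule for the men affected.

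**Conclusion.** The concern holds as an inexpensive improvement that should be made, with medium confidence. Followed as written, the plan randomises men before it is known whether there are two spared bundles to cover, and it permits the operator to know the arm while dissecting them. The textual basis is firm: one table mark at Consult, a paragraph that reads as preoperative, a no-tissue control, eligibility on scheduled sparing, and no statement that withholds the arm.

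The size is unknown. The figures show only what would follow from an SD of 6.71, shifts of 0.5 to 2 points and incomplete sparing in 5 to 20% of men, none of which the document states. They do not measure a defect. The case for change is that any handling bias could not be corrected at analysis, whereas withholding the arm until dissection is complete removes the opportunity for it.

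**What to change.** 1. Keep consent and baseline questionnaires before surgery. Open the allocation on the surgical day, for example in REDCap (already used for the questionnaires), only after the operator has recorded each bundle as spared or not spared by a definition written into the protocol.
2. Either move the randomisation mark to Surgical Day and amend the paragraph, or leave it and state that any earlier list is concealed from the operator until that entry is made.
3. Add sparing on each side to the operative items recorded.
4. Analyse all randomised men in their assigned arm.
5. If randomisation itself moves, log men without both bundles spared as not randomised, with the reason. If it stays preoperative, keep them in the analysis and state whether LPT is placed.

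If an allocation step in theatre is not feasible, points 3 and 4 and the placement rule in point 5 still settle how these men are handled, but the opportunity for handling bias remains.

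The cost is some wording, one data field, a brief step in theatre and product on hand for every case. If randomisation moves, a few consented men will not be randomised, and the result will apply to men with achieved bilateral sparing.

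### The primary IIEF outcome is listed at six visits under an unspecified ANOVA, so the stated alpha and power, given for 6 months only, are not tied to a declared primary comparison

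*Combined protocol and SAP*

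**What the plan says.** All statements on the primary analysis stand in Section 5 (Study Statistics) of the combined protocol and SAP.

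- **Outcome.** The primary variable is the "score on the IIEF questionnaire (erectile function domain) at 1,3, 6, 9, 12 and 18 months post-surgery". The six visits have equal standing.
- **Decision language.** The only sentence on efficacy is "Comparison of changes in initial IIEF score will be evaluated to determine treatment efficacy". It names no visit, test or threshold.
- **Method, alpha and power.** "For statistical analysis based on ANOVA, the sample size is powered for a power of 80% with one-sided alpha of 0.05". The form of ANOVA is not given.
- **Effect and size.** The calculation concludes that "a sample size of 23 patients in each arm is necessary" to detect 5 points (20 against 15) at 6 months. Enrolment is then set at 30 per arm to allow for dropout. No standard deviation is given.
- **Baseline.** Section 2 (Study Procedures) provides for "baseline evaluation including medical clearance and completion of validated questionnaires", and its schedule shows the IIEF at consultation and at every visit listed in Section 5.

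No other section names a deciding visit, a summary across visits, an order of testing or a multiplicity rule.

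**The concern.** A one-sided 5% error rate and 80% power are properties of one specified test. Here they appear only in the sentence that justifies the sample size, which says what a given number of patients could detect at 6 months, not which comparison decides the trial.

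The text supports more than one later reading. The powering sentence points to 6 months. The expectation of a gradual rise in score over the study, together with ANOVA, could point to a longitudinal test. The motivating study in Section 1 reports potency at 8 weeks and a mean recovery time of 1.34 months, which could point to the early visits.

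If the choice is made after the data are seen, a positive result cannot be tied to the stated 5%, nor a negative one to the stated 80%. Such a choice cannot be repaired credibly afterwards.

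**Working it through.** **1. Inputs.** From Section 5: difference 5 points, one-sided alpha 0.05, power 80%, 23 per arm, six primary visits. Not in the documents, so assumed: the SD, the correlation between visits, and the correlation of baseline with the 6-month score.

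**2. The plan's own figure.** Without an SD, 23 per arm can only be solved backwards. For a two-sample t-test with n per arm, power = P(T > t₀.₉₅,₂ₙ₋₂), where T is noncentral t with noncentrality d·√(n/2) and d = 5/SD.

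- n = 23: 44 degrees of freedom, critical value 1.680. Power of 0.80 needs noncentrality 2.526, so d = 2.526/√11.5 = 0.745 and SD = 5/0.745 = 6.71.
- n = 22: power of 0.80 needs d = 0.762, so SD = 6.56.

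So 23 is the smallest sufficient number for SDs between about 6.56 and 6.71. With SD 6.71, power is 0.800 at 23 evaluable per arm and 0.886 at 30. The figure is thus consistent with one raw-score comparison at one visit. It does not size a test across six visits or a repeated-measures contrast.

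**3. What each reading implies.**

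| Reading of Section 5 | False-positive chance | Does the stated power apply? |
|---|---|---|
| One test at 6 months | 5% | Yes, at 23 evaluable per arm and SD about 6.7 |
| One repeated-measures test | 5% | No, it needs its own calculation |
| Success at any of six visits (not stated in the plan) | see step 4 | No |

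**4. Illustration of the any-visit reading.** With independent visits the chance of at least one false positive is 1 − 0.95⁶ = 0.265, which is not realistic for repeated scores on the same patients. With equal correlation ρ between visits and normal test statistics it is 1 − ∫ φ(c)·Φ[(1.645 − √ρ·c)/√(1 − ρ)]⁶ dc. A simulation with two-sample t-tests at 23 per arm agrees closely:

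| Assumed ρ | Integral | Simulated t-tests |
|---|---|---|
| 0.3 | 0.220 | 0.219 |
| 0.5 | 0.186 | 0.187 |
| 0.7 | 0.148 | 0.150 |
| 0.9 | 0.100 | 0.103 |
| 0.95 | 0.084 | 0.083 |

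**5. Baseline adjustment at 6 months.** Adjusting for baseline multiplies the residual variance by 1 − r², where r is the correlation of baseline with the 6-month score, and costs one degree of freedom. Simulated ANCOVA power at 23 per arm (difference 5, SD 6.71), against 0.80 for the raw score:

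| Assumed r | ANCOVA power |
|---|---|
| 0.1 | about 0.79 |
| 0.3 | about 0.83 |
| 0.5 | about 0.88 |
| 0.7 | about 0.96 |

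**The case against.** **Six months is already implied.** Alpha, power, difference and sample size are all given for that visit and for no other. This stands, and it narrows the freedom of choice. It does not remove it, because Section 5 gives all six visits the same primary status and never says that the 6-month comparison decides.

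**A method is named.** ANOVA over six visits could mean one repeated-measures test, which would hold error at 5%. This also stands as a possible reading. But the form is not stated, and the stated calculation does not size such a test.

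**Score against change is not a contradiction.** The score can be the variable and change the comparison, and in randomized arms the expected 5-point difference is the same on either scale. That is fair. The form does affect power: the SD of change is 6.71·√(1 + k² − 2rk), where k is the ratio of baseline SD to 6-month SD. With k = 1 and r from 0.1 to 0.7, change-score power runs from 58% to 94%. But Section 3 admits only men with IIEF-5/SHIM of at least 18, which narrows the baseline spread and makes k = 1 doubtful. With k = 0.25 the range is about 80% to 91%. The baseline question is therefore a reason to specify the form, not evidence of large lost power.

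**Stronger readings to avoid.** A reader might infer that the trial plans to claim success at any visit and so carries a false-positive rate of 8 to 22% or more. The documents state no such rule, and every correlation behind those figures is assumed. A reader might also bring in the low power that 10 per arm (Section 2) would give. The conflict between 10 and 30 per arm must be reconciled, but it is a separate matter and has no bearing on which visit decides.

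**Conclusion.** The point holds as an undeclared primary comparison. Section 5 lists six primary visits and an ANOVA of unstated form, and attaches its alpha and power to 6 months without making that visit the test. This rests on the text alone and needs no assumption.

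The size of the consequence does rest on assumptions. An any-visit rule would give about 8 to 22% false positives for equal correlations from 0.95 down to 0.3, against 5% for a single declared test. That range shows what the open choice could permit; it is not an error rate of this plan. The stated 80% power applies only if the 6-month comparison is the test, 23 per arm are evaluable, and the SD is near the back-solved 6.7.

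**What to change.** In Section 5, name the between-arm comparison of the IIEF erectile function domain at 6 months, adjusted for the baseline IIEF score (ANCOVA, in place of an unspecified ANOVA or change comparison), as the single primary analysis at the stated alpha. Make 1, 3, 9, 12 and 18 months secondary, reported with estimates and confidence intervals or tested after 6 months in a prespecified order. Six months is suggested because the sample size already refers to it.

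If a repeated-measures ANOVA was intended, state its one primary contrast and give a power calculation for that contrast, including the assumed SD and between-visit correlation.

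The change takes two or three sentences and should be made before outcome data are examined by arm. Visits and data collection stay as they are, since the baseline IIEF is already collected. There are two downsides: the other five visits can no longer support the primary claim, and ANCOVA loses about 1 point of power at 23 per arm if baseline correlates only about 0.1 with the 6-month score.
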